7.1.3 Investigational Product Handling and Disposal

The Investigator or designee must either destroy unused IP on site or return any unused IP to the Sponsor or designee, regardless of whether the study was completed or terminated prematurely. Destruction or return of IP must be appropriately documented.

7.2 Additional Study Medication

7.2.1 Oral Glucocorticoid Taper

All subjects will receive daily oral prednisone (or equivalent) from Day 1 through Week 8, according to a tapering dose schedule (Table 9). The open-label GCs will be local, commercial products supplied to subjects by the investigational sites.

Table 9Glucocorticoid Taper Schedule (Randomized-controlled Period)

RCP Week	Oral Prednisone Dose (or Equivalent)
Weeks 1-2	20 mg/day
Weeks 3-4	15 mg/day
Weeks 5-6	10 mg/day
Weeks 7-8	5 mg/day

RCP = randomized-controlled period.

7.3 Assessment and Verification of Compliance

Site staff will administer the infusion IPs at the study center. The dose and date of administration of IP must be recorded in the subject eCRF. Treatment compliance for IV inebilizumab and IV placebo will be assessed based on this information.

Patients are to bring their prednisone (or equivalent) tablets with them each visit until the end of the 8-week GC taper so that a compliance check (pill count) can be performed. An assessment of compliance will be recorded by the study staff in source documentation.

7.4 Treatment Assignment and Bias Minimization

7.4.1 Treatment Allocation for RCP

Subjects will be randomized 1:1 within each stratum (by first or subsequent IgG4-RD manifestation, ie, newly-diagnosed vs recurrent) by the IXRS to either the inebilizumab group or the placebo group.

- Inebilizumab group: Inebilizumab 300 mg IV on Day 1, Day 15, and at Week 26
- Placebo group: Matching IV placebo on Day 1, Day 15, and at Week 26

7.4.2 Treatment Allocation for OLP

All subjects in the OLP will receive open-label inebilizumab 300 mg IV on Day 1 and at Week 26. On Day 15, subjects who were randomized to receive inebilizumab in the RCP will receive a blinded dose of IV placebo, while subjects who were randomized to receive placebo in the RCP will receive a blinded 300 mg dose of inebilizumab. This allocation will be managed by the IXRS to maintain the blinding of sites and subjects to treatment assignment during the preceding RCP. Subsequent administrations of 300 mg IV inebilizumab will occur every six months for the remainder of the OLP.

7.4.3 Randomization Strategy and Procedure

An IXRS will be used for randomization to a treatment group and assignment of IP kit numbers. A subject is considered randomized into the study when the Investigator notifies the IXRS that the subject meets eligibility criteria and the IXRS provides the assignment of treatment group.

Additional details are provided in the IXRS manual.

7.4.4 Extent and Maintenance of Blinding

This is a double-blind study in which inebilizumab and placebo are matched in appearance.

The Sponsor will remain blinded until after the database lock for primary efficacy analysis, which will occur after all subjects have completed the Day 365 visit (Visit 15) or discontinued early from the RCP. Subjects, site staff, and contract research organization (CRO) personnel will remain blinded to individual subject treatment assignment until final database lock at the conclusion of the study. Potentially unblinding laboratory data will not be available to investigative site personnel until after final database lock.

If treatment allocation for a subject becomes known to the Investigator or other study staff involved in the management of study subjects, the Sponsor must be notified immediately.

7.4.5 Unblinding Procedures

In the event of a medical emergency, the Investigator may unblind an individual subject's IP allocation. Instructions for unblinding an individual subject's IP allocation are contained in the IXRS manual. In general, unblinding should only occur if management of the medical emergency would be different based on the subject having received IP. In the majority of cases, the management of a medical emergency would be the same whether or not IP was received by the subject. If this was the case, the IP allocation should not be unblinded.

7.5 Concomitant Medications and Treatments

Subjects should receive all medications, including treatments for IgG4-RD, that are considered by their physician to be necessary for their health and well-being.

The Sponsor recommends that Investigators ensure that all patients are up to date with required vaccinations prior to entry into the study.

7.5.1 **Prohibited Medications**

Patients must receive all treatments that are considered necessary for their health in the judgment of their physician(s). The following prohibited medications will require the discontinuation of IP, but subjects who receive prohibited medications must remain in the study through the final Week 52 RCP visit.

Generally, GC treatment for reasons other than new or worsening IgG4-RD activity is prohibited, but exceptions are described in Section 7.5.2 (GCs for uses other than IgG4-RD). The per-protocol limitations on dose and duration of GC treatment for IgG4-RD flare are described in Section 7.6. The Investigator must provide the indication for each use of GC or other immunosuppressive therapy.

Additional prohibited medications in the RCP and OLP include:

- Biologic or non-biologic immunosuppressive agents other than GCs, including but not limited to, azathioprine, mycophenolate mofetil, cyclosporine, methotrexate, leflunomide, cyclophosphamide, rituximab, etanercept, adalimumab, infliximab, certolizumab pegol, golimumab, abatacept, and tocilizumab.
- Live viral vaccines or live therapeutic infectious agents.

Receipt of prohibited medication requires discontinuation of IP as described in Section 6.4.1.

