5.2 Exclusion Criteria

Any of the following excludes an individual from participation in the study:

- 1. Severe cardiovascular, respiratory, endocrine, gastrointestinal, hematological, neurological, psychiatric, or systemic disorder, or any other condition that, in the opinion of the Investigator, would place the patient at unacceptable risk of complications, interfere with evaluation of the IP, or confound the interpretation of patient safety or study results.
- 2. History of solid organ or cell-based transplantation.
- 3. Known immunodeficiency disorder.

- 4. Active malignancy or history of malignancy that was active within the last 10 years, except as follows:
 - In situ carcinoma of the cervix following apparently curative therapy > 12 months prior to screening,
 - Cutaneous basal cell or squamous cell carcinoma following apparently curative therapy,
 - Prostate cancer treated with radical prostatectomy or radiation therapy with curative intent > 3 years prior to screening and without known recurrence or current treatment, or
 - Thyroid cancer for which surgery has been performed and there is no evidence of active disease.
- 5. Receipt of any biologic B cell-depleting therapy (eg, rituximab, ocrelizumab, obinutuzumab, ofatumumab, inebilizumab) in the 6 months prior to screening.
- 6. Receipt of non-depleting B-cell-directed therapy (eg, belimumab), abatacept, or other biologic immunomodulatory agent within 6 months prior screening.
- 7. Receipt of non-biologic DMARD or immunosuppressive agent other than GCs (eg, azathioprine, mycophenolate mofetil, methotrexate, others) within 4 weeks prior to screening.
- 8. Receipt of any investigational agent < 12 weeks or < 5 half-lives of the drug (whichever is longer) prior to screening.
- 9. Inability to be tapered off of GC therapy by 8 weeks post-randomization (other than ≤ 2.5 mg/day prednisone or equivalent for treatment of adrenal insufficiency or intolerance of taper) in the opinion of the Investigator.
- 10. Receipt of live vaccine or live therapeutic infectious agent within the 2 weeks prior to screening.
- 11. Pregnancy, lactation, or planning to become pregnant within 6 months of the last dose of IP.
- 12. Positive test for, or prior treatment for, hepatitis B or HIV infection. A positive test for hepatitis B is detection of either (1) hepatitis B surface antigen (HBsAg); or (2) hepatitis B core antibody (anti-HBc); and in Japan only (3) hepatitis B surface antibody (HBsAb)

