6.2.3 Schedule of OLP Assessments and Procedures

6.2.3.1 Eligibility for OLP

Subjects eligible for the OLP must:

- 1. Have completed the RCP Week 52 visit (end of RCP).
- 2. Must not have had IP discontinued for any of the following safety reasons:
 - Anaphylaxis or a serious hypersensitivity reaction that occurred within 7 days after IV dosing and cannot be attributed to another known allergen exposure (see Appendix B).
 - Any adverse event (AE) or significant laboratory abnormality that, in the opinion of the Investigator, Sponsor, or SDMC, warrants discontinuation of dosing.
 - Any life-threatening (Grade 4) infection.
 - Any event of sepsis or febrile neutropenia.
 - Any infection listed as either a definite or probable opportunistic infection in Appendix A.
 - Any Grade 3 IRR.
 - Any Grade 4 serious adverse event (SAE).
 - Pregnancy or a decision to become pregnant.
 - Malignancy.
 - Absolute neutrophil count < 800 cells/ μ L confirmed by repeat testing.
 - Determination that the subject was ineligible for study participation and continuation of IP could pose a safety risk to the subject in the judgment of the Investigator or Sponsor.
 - Significant noncompliance with the study protocol, as judged by the Investigator or Sponsor.
 - Receipt of any B cell-depleting therapy (eg, rituximab, ocrelizumab, obinutuzumab, ofatumumab, commercially available inebilizumab).
- 3. Have completed a 28-day washout period after discontinuation of non-B cell-depleting, non-GC immunosuppressive therapy initiated during the RCP, if relevant.
- 4. Receive Dose 1 in the OLP within the window of 1-38 days after the RCP Week 52 visit (the final visit for the RCP and the first visit for the OLP cannot occur on the same day).
- 5. Have a planned taper of GCs to discontinuation by 8 weeks after OLP Dose 1, if receiving GC at the time of OLP entry.

To maintain the every-6-month dosing of IP, subjects should enroll in the OLP and be dosed as soon as is feasible after completion of the RCP. All SAEs and AEs that occur between the end of the RCP and start of the OLP must be collected at OLP Visit 1. Investigational product discontinuation rules apply during the OLP (Section 6.4.1).

Table 5 summarizes the schedule of procedures for the OLP.

Study Period					Open-Lal	oel Perio	d						
OLP Visit Number	OLP V1	OLP V2	OLP V3, V4	OLP V5	OLP V6, V7	OLP V8	OLP V9, V10	OLP V11	OLP V12, V13	OLP V14	OLP V15, 17, 19, 21	OLP V16, 18, 20,	OLP V22/EDV

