6.4 Discontinuation of Investigational Product, Withdrawal from Study, and Loss to Follow-up

6.4.1 Discontinuation of Investigational Product

IP must be discontinued if the Investigator determines that continuing it would result in a significant safety risk for that subject. The following events require discontinuation of IP:

- 1. Anaphylaxis or a serious hypersensitivity reaction that occurred within 7 days after IV dosing and cannot be attributed to another known allergen exposure (see Appendix B).
- 2. Any AE or significant laboratory abnormality that, in the opinion of the Investigator, Sponsor, or SDMC, warrants discontinuation of dosing.
- 3. Any AE of immune complex disease.
- 4. Any life-threatening (Grade 4) AE.
- 5. Any event of sepsis or febrile neutropenia.
- 6. Any infection listed as either a definite or probable opportunistic infection in Appendix A.
- 7. Any Grade 3 AE with the following exceptions:
 - A Grade 3 AE of flare or exacerbation of IgG4-RD (per protocol, these events are not reported as SAEs as they may represent the primary endpoint of the study)
 - A Grade 3 event that is not an IRR or infection, does not meet any other discontinuation criterion, and for which the SDMC has agreed that IP dosing can continue
- 8. Pregnancy or a decision to become pregnant.
- 9. Malignancy.
- 10. Absolute neutrophil count < 800 cells/µL confirmed by repeat testing.
- 11. Withdrawal of consent for further study participation or for further receipt of IP.
- 12. Receipt of prohibited medication(s) (see Section 7.5.1).
- 13. Determination that the subject was ineligible for study participation and continuation of IP could pose a safety risk to the subject in the judgment of the Investigator or Sponsor.
- 14. Significant noncompliance with the study protocol, as judged by the Investigator or Sponsor.

Severity of AEs will be graded according to the National Cancer Institute Common Terminology Criteria for Adverse Events (CTCAE) (Section 8.1)

Subjects with Grade 3 SAEs should have their AE data reviewed by the Investigator to specifically address whether or not IP should be discontinued or delayed to ensure patient safety, particularly for Grade 3 SAEs of infection (Section 7.1.1.4). The medical monitor(s) and the SDMC are available for discussions regarding suitability of repeat dosing in a subject who has had a Grade 3 SAE.
Clinical Study Protocol	Horizon Therapeutics Ireland DAC
VIB0551.P3.S2 - MITIGATE	Inebilizumab

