Amendment 9.1, 08AUG2023	IgG4-Related Disease

The reason(s) for discontinuing IP must be recorded on the appropriate page of the eCRF. If subjects choose to discontinue IP, the reason, such as an AE, lack of efficacy, or other reason, must be recorded in the eCRF.

Subjects who discontinue IP during the RCP should remain in the study and complete all RCP study visits, assessments, and procedures (with the exception of IP administration and associated

unless they have withdrawn consent for study participation or withdrawn consent for specific assessments (if subjects will not agree to return for visits, safety data can be collected by telephone call if subjects agree).

Subjects who discontinue IP during the RCP may be eligible to enroll in the OLP, if they meet criteria outlined in Section 6.2.3.1. Site Investigators will be trained about the importance of retention of subjects through the completion of the RCP, and patients will be informed about the continued scientific importance of their data even if they discontinue study treatment early.

Subjects who do not participate in the OLP, and subjects who discontinue IP during the OLP, will be asked to return to the clinic for a series of visits occurring every six months for a total of two years after their last dose of IP. These post-discontinuation follow-up visits will include a limited set of assessments including CD20+ B cell counts, immunoglobulins levels, concomitant medications, and adverse events. These visits are described in detail in Section 6.2.4, Safety Follow-Up Period.

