7.1.1.4 Investigational Product Dosing and Administration

Prior to each infusion in the RCP and OLP, the Investigator or other qualified medical personnel must confirm that none of the conditions requiring delay or discontinuation of IP administration are met (Section 6.4.1).

Premedication (from commercial supplies) with a corticosteroid (eg, methylprednisolone 100 mg IV or equivalent), an antihistamine (eg, diphenhydramine 25-50 mg orally or equivalent), and an anti-pyretic (eg, acetaminophen 500-650 mg orally or equivalent) will be administered approximately 30-60 minutes prior to each IP infusion.

Vital signs will be obtained prior to the start of each IP infusion. An experienced and qualified staff member will place the IV access.

The prepared solution will be administered IV via an infusion pump at an incrementally increasing rate through an IV line containing a sterile, low-protein binding 0.2 or 0.22 micron in-line filter according to the schedule in Table 8.

Table 8Infusion Rate for Investigational Product after Dilution in a 250 mL IV
Bag

Elapsed Time (minutes)	Infusion Rate (mL/hour)
0-30	42
31-60	125
61 to end of infusion	333

IV = intravenous.

Clinical Study Protocol	Horizon Therapeutics Ireland DAC
VIB0551.P3.S2 - MITIGATE	Inebilizumab
Amendment 9.1, 08AUG2023	IgG4-Related Disease

Unless an infusion reaction occurs resulting in discontinuation of infusion, the entire infusion bag contents must be administered and the tubing must be flushed with a volume of saline at least as large as that of the tubing to ensure complete delivery of the IP infused at a rate not to exceed 333 mL/hour.

After completion of the infusion, subjects will be observed for at least one hour.

Medically qualified personnel must be immediately available to respond to emergencies during administration of IP. Appropriate drugs and medical equipment to treat acute hypotensive, bronchoconstrictive, or anaphylactic reactions must be immediately available, and study personnel must be trained to recognize and treat these reactions. Additionally, appropriate drugs and medical equipment to treat IRRs must be immediately available, and study personnel must be trained to recognize and treat these reactions.

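### Section 7.5.1 bans live *viral* vaccines on study while exclusion 10 covers any live vaccine, so a prophylactic live bacterial vaccine does not, on the literal wording, trigger the automatic IP stop

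*Protocol*

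**What the plan says.** **On-study rule.** Protocol Section 7.5.1 lists additional prohibited medications for the RCP and OLP. The second bullet is "Live viral vaccines or live therapeutic infectious agents".

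**Entry rule.** Section 5.2, criterion 10, excludes for "Receipt of live vaccine or live therapeutic infectious agent within the 2 weeks prior to screening". The first limb carries no *viral* qualifier.

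**Mandatory stop.** Section 6.4.1 item 12 requires IP to stop for "Receipt of prohibited medication(s) (see Section 7.5.1". Section 7.5.1 points back to 6.4.1, so the scope of item 12 is whatever 7.5.1 prohibits.

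**General rule.** Section 6.4.1 opens with a wider provision: "IP must be discontinued if the Investigator determines that continuing it would result in a significant safety risk for that subject". Under Section 7.1.1.4, before each RCP and OLP infusion, the Investigator or other qualified personnel "must confirm that none of the conditions requiring delay or discontinuation of IP administration are met".

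**After a stop.** Section 6.4.1 says: "Subjects who discontinue IP during the RCP may be eligible to enroll in the OLP", subject to Section 6.2.3.1. The reasons for discontinuation that bar OLP entry include "Receipt of any B cell-depleting therapy (eg, rituximab, ocrelizumab, obinutuzumab, ofatumumab, commercially available inebilizumab"; none names a vaccine. They also include significant noncompliance as judged by the Investigator or Sponsor.

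**The concern.** The two rules are worded almost alike, but the on-study one is narrowed by a single word, and neither document explains why. After a live viral vaccine the stop is automatic. After a prophylactic live bacterial vaccine, the next dose depends on someone's judgment.

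Serious infection is a stated potential risk of inebilizumab (Section 2.1.4), and serious and/or opportunistic infections are AESIs (Section 8.4). Appendix A includes bacterial infections, such as tuberculosis and invasive salmonellosis, among those that stop IP, so the protocol's interest in infection is not confined to viruses. The Investigator would make the judgment blinded, without post-randomization B-cell results and, until OLP Week 26, without serum immunoglobulin results (Section 6.1.2). What is at stake is uniform handling of a safety rule across sites, not an efficacy result.

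**Working it through.** The plan states no figure on this point, so the check is a reading of the text followed by a count of infusions.

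**1. Classify the product under each rule**

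| Product given on study | Live vaccine (exclusion 10 wording) | 7.5.1, viral-vaccine limb | 7.5.1, therapeutic limb | Item 12 triggered on literal reading |
|---|---|---|---|---|
| Live viral vaccine | yes | yes | – | yes |
| Live bacterial agent given as therapy | – | no | yes | yes |
| Prophylactic live bacterial vaccine | yes | no | no | **no** |

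Only the third row falls through.

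**2. Look for other text that closes the gap**

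The remaining vaccine text (Table 3 with footnote b, and the opening of Section 7.5) concerns vaccination history and being up to date before entry. None of it bars a live bacterial vaccine on study.

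**3. List the routes to a stop that remain**

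- The Investigator's general safety-risk rule in 6.4.1, checked before each infusion under 7.1.1.4.
- Item 2 of 6.4.1: the Investigator, Sponsor or SDMC may stop IP for an adverse event or significant laboratory abnormality.
- An infection that itself meets a stop rule: sepsis, an Appendix A infection, a Grade 3 infection, or any Grade 4 event. The note after Appendix A also lets the Investigator treat further infections as requiring discontinuation.

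None is triggered by the vaccination alone without someone's judgment.

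**4. Count the later infusions that one vaccination could affect**

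Formula: infusions scheduled in the period, minus the first.

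- RCP (Table 4): Day 1, Day 15, Week 26. 3 − 1 = **2** later infusions: 2 active in the inebilizumab arm, 0 in the placebo arm.
- OLP (Table 5): Weeks 0, 2, 26, 52, 78, 104, 130. 7 − 1 = **6** later infusions: 6 active in former placebo subjects. For former inebilizumab subjects it is 6 − 1 = 5, because under Section 7.4.2 "On Day 15, subjects who were randomized to receive inebilizumab in the RCP will receive a blinded dose of IV placebo".
- Windows with no infusion left in the period, if dosing is on schedule: RCP 52 − 26 = 26 weeks; OLP 156 − 130 = 26 weeks.

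Two of these figures are not firm:

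- Table 4 footnote e allows the Week 26 dose to be delayed with Sponsor agreement, which shortens the RCP window.
- If IP were discontinued in the RCP for significant noncompliance, OLP entry would be barred and the 7 OLP infusions lost as well: 2 + 7 = 9 at most.

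**5. Check the analyses**

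The primary analysis uses all RCP data (protocol 9.5.1; SAP 3.5.1.1). The additional analysis censors for IgG4-RD treatment or for prohibited GC or immunosuppressive treatment (protocol 9.5.1; SAP 3.5.1.2). A vaccine is neither, so the definitions are unaffected with or without the edit.

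**The case against.** **The list may be open-ended.** Its lead-in uses *include*, and *therapeutic* is not defined, so a site could treat a prophylactic live bacterial vaccine as prohibited. This stands as a possible reading. But the immunosuppressant bullet in the same list carries an explicit non-limiting phrase and the vaccine bullet does not. A site could fairly take *viral* as deliberate, and a mandatory stop should not turn on which reading a site adopts.

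**The rules have different jobs.** Exclusion 10 is a pre-screening restriction and 7.5.1 triggers discontinuation, so identical scope is not required. Leaving an uncommon product to medical judgment could be a choice. That is fair, but the documents do not state such a choice.

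**Controls already exist.** This largely stands. Concomitant medications are reviewed at every RCP visit and OLP contact, so a vaccination would be recorded, and the routes in step 3 remain. The residual gap is a vaccinated subject with no adverse event whom nobody judges to be at significant risk.

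**Appendix A proves little.** It stops IP for infection, not for exposure to a vaccine. It shows concern about bacterial disease but not an intended ban on bacterial vaccines. Agreed; it is context only.

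**Withholding a dose does not quickly undo depletion.** In Study 1155, B-cell counts were still below the lower limit of normal in 94% of subjects at 28 weeks (Section 4.2). So the infusion count is an imperfect measure of benefit. Section 7.5.1 also tells sites what not to give, and that instruction helps even when no infusion remains.

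**Conclusion.** The wording gap is real in the current text and worth closing, at the lowest level of importance. It rests on the literal reading of 7.5.1 and on *therapeutic* not covering prophylaxis. The documents name no live bacterial vaccine that these subjects would receive.

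Three stronger inferences are not supported:

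- **That the protocol bans nothing but live viral vaccines here, or leaves these subjects without a control.** The same bullet also covers live therapeutic agents, and the general rule, item 2 and the infection stop rules all remain. Only the automatic stop is missing.
- **That the trial's efficacy conclusions are at risk.** No endpoint, estimand, sample size or alpha depends on vaccination.
- **That the exposure is strictly capped at 2 infusions in the RCP.** That is the usual count. It assumes the subject can still enter the OLP, and the 26-week window assumes on-schedule dosing.

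Confidence is high in the wording difference and its consequence for item 12. The documents do not demonstrate any effect on patients.

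**What to change.** In Section 7.5.1, delete the word *viral*, so that the bullet begins *Live vaccines or* and is otherwise unchanged. It then matches the product wording of exclusion 10, and 6.4.1 item 12 follows through its existing cross-reference with no further edit.

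**Cost.** A one-word amendment, a site notice, and a rare extra IP discontinuation: normally up to 2 later infusions in the RCP or 6 in the OLP for that subject. A subject stopped in the RCP stays in the study through the Week 52 visit. That subject may still enter the OLP unless IP was discontinued for a barred reason such as significant noncompliance (Section 6.2.3.1). A subject stopped in the OLP moves to the existing two-year safety follow-up (Section 6.2.4). No new data or procedures are needed.
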